# 10 STATISTICS

#### 10.1 Methods and Planning

Only descriptive analyses will be performed.

All analyses will be performed on all treated patients, and will be presented by dose (1 mg/kg, 2 mg/kg, 4 mg/kg and 10 mg/kg). Analyses will be performed using SAS 9.3 or a later version.

A statistical analysis plan (SAP) will be prepared as a separate document and will include a more technical and detailed description of the planned statistical analyses. The SAP will be finalized before database lock.

#### 10.2 SAMPLE SIZE

36 to 48 patients will be enrolled in this clinical study:

Up to 24 patients (3 to 6 patients at each dose level) will be enrolled in the dose-escalation phase Ib Up to 24 patients in the phase IIa

The 3 to 6 patients treated during the phase Ib with the phase IIa recommended dose will be included in the efficacy analysis set of the phase IIa part.

If 6 patients (3+3 for safety reasons) are treated during the phase Ib with the phase IIa recommended dose, a maximum of 21 patients will be included in the phase IIa

If 24 patients were enrolled in the phase Ib of the trial (including 6 at the recommended dose of the phase IIa, no more than 21 patients would need to be enrolled in the phase IIa; Which means than the total number of patients will never exceed 45 (24+21)

Primary efficacy endpoint: CR rate based on IWCLL criteria

The significance level (alpha risk) is set at 0.05 and power of at least 80%. The one-sided null hypothesis is specified as H0: p = 0.05 and the alternative H1: p= 0.20, p the probability to achieve a CR

Further investigation is deemed warranted if  $\geq$  4 patients achieve a CR by the end of the study ( $\geq$  4/27).

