### Sample size:

36 to 45 patients will be enrolled in this clinical study:

- o 12 to 24 patients (3 to 6 patients at each dose level) will be enrolled in the dose-escalation phase lb
- o Up to 24 patients in the phase IIa.

The 3 to 6 patients treated during the phase Ib at the recommended dose for the phase IIa will be included in the efficacy analysis set of the phase IIa part.

If 6 patients (3+3 for safety reasons) are treated during the phase Ib with the recommended dose for the phase IIa, a maximum of 21 patients will be included in the phase IIa; otherwise 24 patients will be included in the phase IIa study.

If 24 patients were enrolled in the phase Ib of the trial, including 6 at the recommended dose for the phase IIa, no more than 21 patients would need to be enrolled in the phase IIa. This means than the total number of patients will never exceed 45 (24+21).

The recruitment of the patients is expected to approximately cover an 18-month period.

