### Statistical methods

Up to 24 patients will be enrolled in the dose escalation phase Ib of the study (3 to 6 patients at each of the 4 dose levels).

After the completion of the part 1, dose escalation phase lb, up to 27 evaluable patients will be treated with IPH2201, as part of the phase IIa of the study, at the dosage recommended at the end of the first dose level. The 3 to 6 patients enrolled during the part 1 of the study, at the dosage recommended for the phase 2 part, may be included in the group of patients used for the assessment of efficacy, thereby reducing the sample size in part 2 from 24 to 21 patients.

Primary efficacy endpoint: complete response rate based on IWCLL criteria.

The significance level (alpha risk) is set at 0.05 and power at 80%. The one-sided null hypothesis is specified as  $H_0$ : p = 0.05 and the alternative  $H_1$ : p = 0.20, p the probability to achieve a CR.

Further investigation is deemed warranted if  $\geq 4$  patients achieve a CR by the end of the study ( $\geq 4/27$ ).

The study could be technically stopped as soon as 4 CRs are documented, but, in that case, accrual of a minimum of 12 patients is recommended to further document safety, pharmacologic endpoints and biomarkers.

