# 3.3.4 Prevention of Tumor Lysis Syndrome

In order to prevent TLS, several preventative measures should be followed in patients participating in the phase Ib part of the study.

- O Hydration: patients should begin per os hydration 3 days before each of the first 4 infusions of IPH2201 (at least 8 full glasses of water -approximately 2 liters daily). On the day of IPH2201 administration, patients should receive IV fluids (at least 1.5 liter of normal saline) during at least 6 hours, from the first to the fourth administration during the phase Ib. Thereafter, in the absence of TLS, the patient should receive IV fluids (at least 1 liter) during 4 hours on the day of each IPH2201 administration
- Daily administration of allopurinol (200-300 mg/ day) should be given 3 days before and 4 days after the first 4 infusions of IPH220 at week 0 and Week 2 visits (IPH2201 alone) and at Week 4 and Week 6 visits (combined therapy)
- Biology should be frequently monitored from the first to the fourth administration of IPH2201, as
  described in the flow chart foot notes, in synopsis and in section 6 (complete blood count with
  differential and comprehensive metabolic panel 4 hours after the beginning of IPH2201 infusion)

Patients may be initially hospitalized in outpatient facilities. Evidences of TLS should lead in any case to keep the patient hospitalized overnight to infuse at least 4 liters of IV fluids /24hr, or perform an EKG, and, if needed, to begin a continuous cardiac monitoring until the improvement of TLS.

Evidence of TLS may lead the investigator to hospitalize the patient overnight during subsequent administrations, and to monitor closely the biochemistry.

In the absence of clinical and biological sign of TLS during the first 4 IPH2201 infusions, these preventative measures will not be necessary for subsequent IPH2201 infusions.

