4.1 General comments

Data will be analyzed using SAS (Version 9.3 or higher). Graphs will be produced in SAS or R.

No tests of significance will be carried out to compare treatment arms on baseline data. Descriptive statistics will be tabulated as follows:

- Categorical data will be summarized in contingency tables presenting frequencies and percentages. By default, those percentages will be calculated on the number of patients in the analysis population.
- Continuous data will be summarized using number of non-missing values (n), mean, standard deviation, median, first and third quartiles, minimum and maximum values.

For phase Ib results, all tables will be presented by dose level and overall. For Phase II, there will be only 1 column. Listings with individual values will be provided for all data presented in the tables.

The patients treated during the phase Ib with the phase IIa recommended dose will be analyzed in all the outputs of both phases of the trial.

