The Kaplan-Meier method will be used to display graphically the DOR, PFS and OS for all patients. The number of patients and the number of DOR, PFS and OS events will also be displayed on the graph. The median (with its 95% confidence interval) DOR and DCOR will be displayed. Listing with individual values will also be displayed.

Page 19 of 26

TPL N°: eTPL SA-02-01

TPL Version: 02

Of SOP SA-02.08 TPL Effective Date: 31 Mar 2016

[figure not shown]

9. Safety Evaluation

All safety analyses will be done for the ITT/safety population.

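### SAP 4.1 gives phase IIa one safety and exposure column that mixes 3 to 6 carried-over phase Ib patients with newly enrolled ones; a second labelled column would separate them

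*Protocol*

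**What the plan says.** **Carry-over for efficacy.** On the 3 to 6 phase Ib patients concerned, protocol 10.2 states: "patients treated during the phase Ib with the phase IIa recommended dose will be included in the efficacy analysis set". The set meant is that of phase IIa. The synopsis (Sample size) and protocol 3.2 say the same. The synopsis section on statistical methods is softer: these patients "may be included in the group of patients used for the assessment of efficacy". SAP 3.3.2 repeats the efficacy-set wording and derives 21 to 24 newly enrolled phase IIa patients from it.

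**Carry-over for everything.** SAP 4.1 says that these patients "will be analyzed in all the outputs of both phases of the trial". On layout it says: "For Phase II, there will be only 1 column". SAP section 9 adds: "All safety analyses will be done for the ITT/safety population". SAP 4.2.1 defines that population as everyone with at least one dose of monalizumab (IPH2201), without regard to phase.

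**What counts as an event.** SAP 4.4 starts the treatment-emergent window at the first dose of any study treatment and ends it 28 days after the last dose of any study treatment.

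**The concern.** The first secondary objective of phase IIa is the safety of the combination. The single column meant to serve it would hold two groups that differ in four ways:

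- **Start.** Phase Ib gives IPH2201 alone at weeks 0 and 2 and adds ibrutinib at week 4. Phase IIa starts both drugs at week 0. Under SAP 4.4, single-agent events from the first 4 weeks enter the combination table.
- **Planned duration.** Protocol 3.4 plans up to 56 weeks of IPH2201 in part 1 and 52 weeks in part 2.
- **Prophylaxis.** Protocol 3.3.4 says that "several preventative measures should be followed in patients participating in the phase Ib part of the study"; no such text is given for phase IIa.
- **Selection.** The carried-over patients belong to a cohort whose own DLT results helped to clear the dose.

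The mixing also reaches tables organised by visit. At the pre-dose week 6 ECG, a phase Ib patient is scheduled to have had 2 weeks of ibrutinib (6 − 4) and a phase IIa patient 6 weeks. Tables of dose delay and discontinuation would combine two suspension schedules, because protocol 3.3.1 sets different ones for the two parts.

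A reader of the phase IIa report could not tell from the column itself how far it describes patients who started the two drugs together.

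**Working it through.** **1. The plan's own design figure.** Inputs from SAP 3.3.2: n = 27, positive if at least 4 CRs, p0 = 0.05, p1 = 0.20, one-sided alpha 0.05, power 0.80. The exact binomial gives P(X ≥ 4 | 27, 0.05) = 0.0437 and P(X ≥ 4 | 27, 0.20) = 0.818. The stated design is reproduced. It concerns efficacy only, and nothing below changes it.

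**2. Share of the column.** 3 carried over + 24 new = 27; 6 + 21 = 27. The shares are 3/27 = 11.1% and 6/27 = 22.2%. Dosed patients who are replaced after early progression stay in the safety population, so the real denominator may slightly exceed 27.

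**3. Effect of the DLT screen on early DLT-type events.** The documents give no DLT rate, so the true rate p is an assumption, taken from 10% to 40% and set equal in both groups to isolate selection. A level clears with 0 of 3, or with 1 of 3 followed by 0 of 3:

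- P(0/3) = (1 − p)³; pooled rate = 24p/27
- P(1/3 then 0/3) = 3p(1 − p)² × (1 − p)³ = 3p(1 − p)⁵; pooled rate = (1 + 21p)/27
- Expected pooled rate = the two rates weighted by these probabilities, divided by their sum

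At p = 0.30 the probabilities are 0.343 and 0.151 (sum 0.494), and the pooled rates are 7.2/27 = 26.7% and 7.3/27 = 27.0%. The weighted mean is 26.8%, a shift of −3.2 points.

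| True rate p | Cleared with 0/3 | Cleared with 1/6 | P(clear) | Expected pooled rate | Shift (points) |
|---|---|---|---|---|---|
| 10% | 8.9% | 11.5% | 0.906 | 9.4% | −0.6 |
| 20% | 17.8% | 19.3% | 0.709 | 18.2% | −1.8 |
| 30% | 26.7% | 27.0% | 0.494 | 26.8% | −3.2 |
| 40% | 35.6% | 34.8% | 0.309 | 35.3% | −4.7 |

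**4. When the shift reverses.** For a cohort cleared with exactly 1 of 6, (1 + 21p)/27 > p when 1 > 6p, that is, when p < 16.7%. At 10% the pooled rate is 11.5%, which is too high.

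**5. The other route to six patients.** A cohort with 0 of 3 may be expanded after the next level fails, and stands if at most 1 of the 3 added patients has a DLT. At p = 0.30 the expected number of events is 0.441/(0.343 + 0.441) = 0.5625, and the pooled rate is (0.5625 + 6.3)/27 = 25.4%.

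**6. Precision of the two denominators.** With zero events, the one-sided 95% upper limit is 1 − 0.05^(1/n): 10.5% at n = 27, 11.7% at n = 24 and 13.3% at n = 21.

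**The case against.** **The protocol does not forbid pooling.** A reader might infer that the protocol limits the carry-over to efficacy, so that SAP 4.1 contradicts it and these patients must come out of phase IIa safety. The text does not support that. The carry-over sentences explain why 21 to 24 new patients suffice and are silent on safety. Protocol 10.1 presents all analyses on all treated patients by dose, and 10.5 makes every dosed patient evaluable for efficacy and safety. Both can be read as allowing pooling at the recommended dose. This objection stands.

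**The bias is easy to overstate.** A reader might take six carried-over patients as a binomial sample with at most one event, which gives pooled rates of 17.8% at 20% and 26.0% at 30%. That condition fits no single 3+3 path: a cohort expanded after a DLT and then cleared has exactly 1 of 6. Nor is the shift always downward (step 4). The screen also covers only DLT-defined events in the first 8 weeks, SAP 9.1 tabulates DLTs for phase Ib alone, and the adverse event tables run far longer. The extra phase Ib visits and the 4 further planned weeks would, if anything, raise event counts. This objection also stands: the net direction for the full tables is not established.

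**Tumor lysis syndrome is a weak example of harm.** Protocol 1.2.4.2 reports none with ibrutinib alone and expects very limited risk with IPH2201 alone.

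**The cohort can be separated, and pooling has value.** Phase Ib tables are by dose level and SAP 4.1 promises individual listings, so counts can be subtracted; medians and quartiles would need recalculation from the listings. It would be wrong to say that pooling adds nothing, because it raises the denominator from 21 to 24 up to 27. This argues for keeping a pooled view, but not for making it the only one.

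**Conclusion.** The point holds as a minor one, a cheap improvement. SAP 4.1 makes the only phase IIa safety and exposure column a mixture of two start schedules, two planned durations, different prophylaxis text and a cohort selected on its own DLT results. The carried-over patients are 11% to 22% of it.

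For early DLT-type events the average shift is downward and modest, from about 0.6 points at a true rate of 10% to 4.7 at 40%, and it can go upward for a cohort cleared with 1 of 6. These figures rest on assumed rates, on equal true rates in the two groups and on clearance by 0/3 or by 1/3 then 0/3. The effect on the full treatment-emergent tables has not been quantified and is probably smaller. The dilution of combination safety by the single-agent period follows from the text and needs no rate assumption.

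The documents do not support the stronger conclusions that the protocol requires exclusion or that the pooled view should be dropped. The efficacy rule is unaffected.

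**What to change.** Amend SAP 4.1 as follows:

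- Keep the carried-over patients in the phase Ib outputs and in the phase IIa efficacy outputs.
- Present the phase IIa safety, exposure and ECG tables in two labelled columns: newly enrolled phase IIa patients, and all patients treated at the recommended dose.
- In the pooled column, flag events that began before the first ibrutinib dose.

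The cost is a short text change and one extra column. The newly enrolled column has 21 to 24 patients, so its zero-event upper limit is 13.3% to 11.7% instead of 10.5%. The pooled column keeps the 27, so no information is lost.

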# 3 STUDY DESIGN

### 3.1 STUDY ENDPOINTS

# 3.1.1 Primary Endpoints

Part 1: phase lb

The primary endpoint will be the safety of 2 repeated administrations of IPH2201 given as a single agent during 4 weeks and, thereafter, given in combination with ibrutinib during 52 weeks:

- Occurrence of DLT and identification, if any, of the MTD, during the administration of IPH2201 as a single agent and given in combination with ibrutinib
- Occurrence of AEs and SAEs

Safety will be assessed using the CTCAE version 4.03, apart from neutropenia and thrombocytopenia which severity will be graded by using the IWCLL grading scale reported in appendix IV. It will include a descriptive analysis of the frequency and severity of AEs, as well as clinical laboratory tests collected to assess lab abnormalities, results of vital sign measurements, electrocardiograms (ECGs), physical examinations and imaging studies. Related AEs will be followed to resolution (≤ grade 1) unless deemed irreversible.

Part 2: phase IIa

The primary endpoint will be the rate of complete response, achieved with a combination of IPH2201 and ibrutinib, assessed 52 weeks after the beginning of the treatment, defined according to the guidelines of IWCLL (Hallek, Cheson et al. 2008), and confirmed by a bone marrow biopsy.

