# 3.1.2 Secondary endpoints

Part 1: phase lb

0

Secondary endpoints are:

- Rate of overall and complete or partial response defined according to the IWCLL guidelines with an additional category of "PR with lymphocytosis" achieved with IPH2201 given as a single agent during 2 cycles, and, thereafter, with the combination of IPH2201 and ibrutinib, and assessed 52 weeks after the initiation of the combined treatment and during the in-study follow-up period.
- Duration of response, PFS and OS. Progression is defined according to the IWCLL guidelines
- with the exception that lymphocytosis cannot be used as the sole criterion for disease progression
- Pharmacokinetic endpoints
  - Concentration at the end (Cinf end) of the 1st to 4th administrations of IPH2201 (every 2 weeks) and thereafter, every at the end of every other administration (every 8 weeks)
  - Accumulation index in terms of Cmax ratio, between 1st administration and selected later administrations
  - Area under the curve from 0 time to 14 days at the 1st (IPH2201 administered alone) and 3rd (IPH2201 and ibrutinib) administrations for patients in the dose escalation phase

CONFIDENTIAL

[figure not shown]
Release date: Edition number

MOD-3783

12 August 2016

GED version

Terminal half-life (T1/2) and clearance (CL) for patients who will complete the study

Secondary endpoints are:

- Rate of complete response defined according to the IWCLL guidelines, documented during the in-study follow-up period of the study.
- o Rate of overall and partial response defined according to the IWCLL guidelines with an additional category of "partial response with lymphocytosis"
- 0
- o Duration of response, progression-free survival (PFS) and overall survival (OS); progression is defined according to the IWCLL guidelines with the exception that lymphocytosis cannot be used as the sole criterion for disease progression
- o Safety of IPH2201: will be assessed using the CTCAE version 4.03 (descriptive analysis of frequency and severity of adverse events); related adverse events followed to resolution (grade ≤ 1) unless deemed irreversible. Safety evaluation will also be based on clinical laboratory tests collected to assess lab abnormalities, as well as results of vital sign

measurements, electrocardiograms (ECGs), physical examinations and imaging studies.

The following endpoints are optional in the phase IIa part of the study

- Pharmacokinetic endpoints

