3.1.2 Phase IIa

3.1.2.1 Primary Objective

The primary objective of the phase IIa is to evaluate the anti-leukemic activity of the combination of monalizumab (IPH2201) and ibrutinib in patients with relapsed, refractory or previously untreated chronic lymphocytic leukemia. The primary endpoint will be the rate of complete response, achieved with a combination of monalizumab and ibrutinib, assessed 52 weeks after the beginning of the treatment, defined according to the guidelines of IWCLL (Hallek, Cheson et al. 2008 [1]), and confirmed by a bone marrow biopsy.

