3.3.2 Phase IIa

The design chosen for the calculation of the sample size is the one-stage Fleming design [2]. The hypotheses are α =0.05 one sided, power of 0.80. The one-sided null hypothesis is specified as H0: p =0.05 and the alternative H1: p= 0.20, p is the probability to achieve a CR. The sample size needed is 27 patients and the trial will be considered as positive if at least 4 CR are observed. The trial will be considered as negative if 3 CR or fewer are observed.

As the 3 to 6 patients treated during the phase Ib with the phase IIa recommended dose will be included in the efficacy analysis set of the phase IIa part, this means that 21 to 24 new patients will be enrolled in the phase IIa. This also means than the total number of patients will never exceed 45 (24+21).

4. General Analysis Definitions

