4.2.2 Main endpoint population

The main endpoint population will include all patients:

Page 14 of 26

TPL N°: eTPL SA-02-01 Of SOP SA-02.08 TPL Effective Date: 31 Mar 2016 TPL Version: 02

Approved in Vault: 3/8/2019

- who have received at least one dose of monalizumab.
- who have received their first dose (W0D1) at least 52 weeks before the data cutoff date.

Patients who discontinued from monalizumab treatment due to disease progression before the end of 8 weeks of treatment will not be part of this population.

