8.1 Rate of complete remission

In both phases, the rate of complete remission is assessed 52 weeks after the initiation of combined treatment

The rate of complete remission (CR) will be calculated in the main endpoint population (see §4.2.2). Within this population, the CR rate will be computed as the number of patients with a confirmed complete remission at W52 divided by the total number of patients in the main endpoint population.

The rate of complete remission with 95% confidence interval will be summarized overall and in the subgroup treated at the RP2D.

In order to claim a CR, the CR must be confirmed. In order to have a confirmed CR (cCR), the CR must be confirmed by a scan and a bone marrow assessment assessed at least 2 months after the first occurrence of CR.

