8.2 Rate of overall and partial remission

The rate of overall and partial remission is assessed 52 weeks after the initiation of combined treatment and during the in-study follow-up.

The rates of overall (i.e cCR, uCR or PR) and partial remission (PR) will be calculated in the main endpoint population (see §4.2.2). Within this population, the overall/partial remission rates will be computed as the number of patients with a any/partial remission at W52 divided by the total number of patients in the main endpoint population.

The rate of overall (and partial) remission will be summarized overall and by dose level and the 95% confidence interval for this rate will be calculated only overall and in the subgroup treated at the RP2D.

The Best Overall Response (BOR) of each patient will be displayed in a summary table. The BOR is the best response (i.e cCR, uCR, PR, SD, PD or NE) taking into account all assessment results until the last disease assessment. The PR does not need to be confirmed and there is no minimum duration for SD. However, a listing with all the derived BOR will be sent to the Sponsor for medical review before the database lock.

Page 18 of 26

TPL N°: eTPL SA-02-01 Of SOP SA-02.08 TPL Effective Date: 31 Mar 2016 TPL Version: 02
Approved in Vault: 3/8/2019

The evolution of tumor response over time will be displayed, separately by patient, via a Swimmer plot (an example of swimmer plot can be found on page 2 of the following document:

Version: 2.0

https://www.pharmasug.org/proceedings/2014/DG/PharmaSUG-2014-DG07.pdf).

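### The phase IIa go rule (at least 4 of 27 CRs) counts CRs to the end of the study in Protocol 10.2, while the primary endpoint and SAP 8.1 count confirmed CR at week 52 and SAP 3.3.2 gives no time point

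*Protocol*

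**What the plan says.** **The decision rule.** Protocol 10.2 and the synopsis (Statistical methods) set the bar at 4 of 27 and count those who, by their wording, qualify when "patients achieve a CR by the end of the study". Protocol 10.3 and the synopsis also allow the study to stop once 4 CRs are documented, with no time point. SAP 3.3.2 says that "the trial will be considered as positive if at least 4 CR are observed" and negative with 3 or fewer. It names no time point and does not say that the CR must be confirmed.

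**The endpoint.** Protocol 3.1.1 defines the phase IIa primary endpoint as a CR rate "assessed 52 weeks after the beginning of the treatment, defined according to the guidelines of IWCLL", confirmed by bone marrow biopsy. SAP 3.1.2.1 matches it: "achieved with a combination of monalizumab and ibrutinib, assessed 52 weeks after the beginning of the treatment". SAP 8.1 takes as numerator "the number of patients with a confirmed complete remission at W52", where confirmation means a scan and a marrow assessment at least 2 months after the CR first occurs. The SAP 4.2.2 denominator is built for the same horizon, admitting those "who have received their first dose (W0D1) at least 52 weeks before the data cutoff date".

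**Later CRs.** Protocol 3.1.2 lists as a secondary endpoint "Rate of complete response defined according to the IWCLL guidelines, documented during the in-study follow-up period of the study". SAP 8.2 also tabulates best overall response (BOR) for each patient, "taking into account all assessment results until the last disease assessment".

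**End of study.** Protocol 3.4 places the End of Study visit 12 months after IPH2201 is stopped and keeps patients on ibrutinib at least until the end of that follow-up.

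**The concern.** The go rule and the endpoint it is meant to judge do not count the same CRs. A CR first reached in follow-up belongs to a secondary endpoint, yet as Protocol 10.2 is worded it helps reach the primary threshold. SAP 3.3.2 does not settle the matter: the SAP yields both a week-52 confirmed count (8.1) and a best response over all assessments (8.2), and 3.3.2 names neither.

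This matters because the trial has one arm. The threshold is the only guard against crediting to IPH2201 the CRs that ibrutinib would have produced alone. Protocol 1.1.5.1 says that ibrutinib's CR rate rises slowly with longer treatment, so a window of about 24 months is easier to pass than one of 12. If the choice of count is left until results are known, the choice could decide the verdict.

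**Working it through.** **1. Reproduce the design.** Inputs from Protocol 10.2 and SAP 3.3.2: n = 27, cutoff 4, p0 = 0.05, p1 = 0.20, one-sided alpha 0.05, power 0.80. With X binomial(27, p):

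P(X ≥ 4) = 1 − Σ C(27, k) p^k (1 − p)^(27−k), k = 0 to 3.

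- p = 0.05: 1 − (0.2503 + 0.3558 + 0.2434 + 0.1068) = 0.0437.
- p = 0.20: 1 − (0.0024 + 0.0163 + 0.0530 + 0.1105) = 0.818.

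An exact search gives 27 as the smallest n meeting both limits (n = 26 has power 0.793). A cutoff of 3 gives alpha 0.150, and a cutoff of 5 gives power 0.652. The stated design is correct. It contains no time point, so anchoring it to week 52 changes none of these figures.

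**2. How far apart the two windows are.** A phase IIa patient completing treatment takes ibrutinib from week 0 to week 52 and then for 12 months of follow-up, about 24 months in all. A phase Ib patient takes it from week 4 to week 56 plus 12 months, also about 24.

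**3. A result that splits the rules.** Take 3 confirmed CRs at week 52 and one more first reached in follow-up.

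| Rule | Count | Threshold met? |
|---|---|---|
| Protocol 10.2, to End of Study | 4 of 27 | Yes |
| SAP 3.3.2 applied to the SAP 8.1 count | 3 of 27 | No |
| SAP 3.3.2 applied to the SAP 8.2 BOR, if the fourth CR is counted there | 4 of 27 | Yes |

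**4. Sensitivity to the ibrutinib-alone rate.** The same formula gives the chance of at least 4 CRs in 27 if IPH2201 adds nothing:

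| Ibrutinib-alone CR rate | P(X ≥ 4) |
|---|---|
| 3% | 0.008 |
| 4% | 0.022 |
| 5% | 0.044 |
| 5.2% | 0.049 |
| 6% | 0.076 |
| 7% | 0.117 |
| 23% | 0.898 |

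The largest rate that keeps this at or below 0.05 is 0.0522.

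The rates in Protocol 1.1.5.1 are, for untreated patients, 6% at 12 months and 23% at 42 months in one study, and 4% at a median of 18 months in another. For previously treated patients they are 3% and 7% at 12 and 42 months. That last sentence speaks of relapses, and reading it as CR is an assumption. No 24-month rate and no planned mix of treated and untreated patients is given.

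**5. Confirmation near week 52.** Two months is about 8.7 weeks, and 52 − 8.7 = 43.3. A CR whose criteria are first met after about week 43 cannot have its SAP 8.1 confirmation in hand by week 52. SAP 8.1 does not say whether it counts.

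**6. Protocol 7.1.** This section requires the CR criteria to be assessed at least 2 months after IPH2201 is discontinued. The last phase IIa dosing visit is W48, and 48 + 8.7 = 56.7, about week 57. For a patient dosed through W48, that does not fit an assessment at week 52.

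**7. Time origin.** Protocol 3.1.1 and SAP 4.2.2 run the 52 weeks from the first dose, whereas SAP 8.1 runs them from the start of combined treatment. In phase IIa these coincide. For the 3 to 6 pooled phase Ib patients, who start ibrutinib at week 4, they differ by 4 weeks.

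**The case against.** The best defence is context. In Protocol 10.2 the rule follows directly on the primary efficacy endpoint, which is fixed at week 52 elsewhere. In the synopsis the next sentence concerns stopping once 4 CRs are documented. The disputed phrase could therefore mean trial completion as opposed to early stopping, not each patient's End of Study visit. SAP 8.1 has one CR numerator, SAP 4.2.2 fits it, and nothing links BOR to the threshold. Protocol 10.1 promises only descriptive analyses, and a late fourth CR would be visible in the BOR table and swimmer plot.

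Much of this is fair. Week 52 is the reading that best fits the SAP. But no passage states the trial-completion reading, and Protocol 3.4 attaches End of Study to a visit a year after IPH2201 stops. The promise of descriptive analyses does not remove a rule with hypotheses, alpha, power and a positive or negative verdict. Displaying a late CR does not say whether it counts.

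Two stronger inferences are not supported:

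- A reader might conclude that the false-positive rate is materially inflated. Linear interpolation of the 12- and 42-month rates to 24 months gives 4.6% for treated patients (3 + 4 × 12/30) and 12.8% for untreated (6 + 17 × 12/30), hence P(X ≥ 4) of 0.034 and 0.46. The interpolation is an assumption, the upper figure needs all 27 patients to be untreated, and the 4% seen at a median of 18 months gives only 0.022.
- A reader might conclude that Protocol 7.1 and the week-52 assessment can never both apply. The synopsis and Protocol 3.3 let IPH2201 end early after a CR with undetectable MRD documented for 2 months. A patient who stops by about week 43 can satisfy both.

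**Conclusion.** The concern holds as a conflict in the decision rule. It is more than a missing detail, because one follow-up CR can change the answer, as step 3 shows. The sample size, cutoff, alpha of 0.0437 and power of 0.818 are all correct.

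The effect on the error rate cannot be sized from the documents. The 5% level requires an ibrutinib-alone CR rate of at most 5.2% in whichever window is counted, and the rate at about 24 months is not given. Nor would anchoring to week 52 guarantee 5%: at the quoted 12-month rate of 6% for untreated patients, the error is already 7.6%. These probabilities assume independent patients with a common CR rate. The documents also do not say whether the quoted rates required the scan and marrow confirmation used in this trial.

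The Protocol 7.1 conflict is limited to patients whose IPH2201 does not end early enough, including all those dosed through W48. The time-origin discrepancy is limited to the pooled phase Ib patients. This should be fixed, but it does not invalidate the trial.

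**What to change.** 1. In the synopsis, Protocol 10.2 and 10.3, and SAP 3.3.2, state that the 4-of-27 threshold counts CRs under the week-52 primary endpoint as computed in SAP 8.1. State that CRs first reached after week 52, including any that appear only in BOR, are secondary and do not count.
2. In SAP 8.1, say whether a CR whose criteria are met by week 52 but whose scan and marrow confirmation falls later is counted, and apply that rule to every patient.
3. Reconcile Protocol 7.1 with the week-52 assessment by stating whether its 2-month interval after IPH2201 discontinuation governs the primary endpoint. If it does, the primary read-out moves to about week 57 or later for patients dosed through W48, and Protocol 10.2, SAP 3.3.2 and SAP 8.1 must move with it.
4. Use one 52-week origin for the pooled phase Ib patients in SAP 8.1 and SAP 4.2.2.

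**Cost.** A protocol amendment, with the ethics review that Protocol 12.2 requires for non-administrative changes, and a SAP revision. No extra patients are needed, and no extra visits if week 52 is kept. Late CRs would no longer help reach the threshold, which is a substantive choice and should be made before the results are known.
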